The design of our intervention requires that we offer stoves that are similar to those offered for the REACCTING study, since we are measuring whether exposure to these technologies through peers influences adoption decisions. However, our experience in the REACCTING study revealed some key challenges with both the Gyapa and Philips stove models, such that we have elected to use slightly different stove models for this project. Through initial lab testing at CU as well as consultation with individuals in the study area, we have selected the Greenway Jumbo stove as a rocket-type stove, similar to the Gyapa, and the ACE1 stove as a forced-draft stove, similar to the Philips.

Peer Effects

Random variation in exposure to peers with cookstove experience will be accomplished through selection of S Group households that vary in terms of their proximity and social contacts with the R Group. The **S1** subgroup will be drawn from the same clusters as the R Group households (25 R Group clusters). S1 group households will thus be located in close physical proximity to R Group households with new stove experience, and are expected to have several social ties to these households. Meanwhile, the **S2** subgroup will consist of 25 clusters randomly selected from the area of the K-N Districts outside of a certain buffer distance from the R Group clusters. Data from the REACCTING study and additional pretesting will be used to select a buffer distance that minimizes the expected number of ties between R and S2 Group households; given that there are more than 300 clusters in the district and only 25 were included in the R Group, these ties are expected to be minimal (and will be measured as part of our data collection). Because the R Group clusters were randomly selected initially, and the S2 clusters will also be randomly selected, the study design ensures that in expectation the only differences between S1 and S2 group households is the former's higher level of exposure to peers with cookstove experience, enabling us to test the impacts of this exposure on our outcomes of interest (perceptions and technology adoption and use).

Prices

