To examine the effects of price (and the interactive effects of prices and peers) on perceptions and technology adoption, both S1 and S2 Groups will be randomly subdivided into multiple price treatment groups. The price randomization will be done at the cluster level – i.e., all households in a cluster will be offered stoves at the same price. Using data from the REACCTING study and pretesting activities, we will set a range of prices for both types of stoves being offered. We will then generate a factorial design that creates different combinations of prices for the two stoves, and randomize these price levels across clusters, balancing prices across **S1** and **S2** clusters. The number of replicates for each price level will be determined to maximize the information expected to be generated from the intervention, using modeling based on parameters derived from pretesting data.

At the given price level, households will choose whether they would like to receive/purchase no stoves, one stove, or two stoves. In addition, households will be able to choose *which type(s)* of stoves they would like: the Gyapa-type (Greenway) or the Philips-type (ACE) stove.

Varying price levels is necessary to our research design and central to our ability to generate one of the key study benefits, namely, information on households' willingness to pay for clean cookstoves in this region. At the same time, we recognize that offering households stoves at different prices has the risk of being seen as creating an unequal burden or inequitable benefits for study participants. Regarding the *burden* for respondents, we emphasize that respondents will be free to choose whether or not to purchase stoves at the given price. This will be emphasized throughout the study, at enrollment and at the time when stoves are offered, and every attempt will be made to ensure that respondents do not feel undue pressure to select to buy a stove. Furthermore, price levels will be set for the two stoves based on an initial phase of focus group and pretesting. Stove prices will be set at or below the actual stove costs –

that is, households will not be asked to pay more than the stoves are actually worth. Finally, we will offer financing options to respondents to allow them to pay for their stoves over time. This may allow some households who would like to buy stoves but face credit constraints in the short term to do so, reducing the burden of paying for stoves all at once.

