Using the cluster-randomized assignment of selected households to different price treatments along with prior random selection of the REACCTING study clusters (and subsequent inclusion of non-REACCTING households), we will estimate a variety of reduced-form and potentially structural models using the exogenous variables of stove price, as well as cluster-level prior adoption and usage. These models will be used to investigate the validity of the broad conceptual model, to test specific research hypotheses emerging from the formal economic model in Section 4.1, and to explore additional research questions, including the relationship between perceived stove quality and instrument-based measures of personal exposure to emissions.

The study's power to detect significant effects will vary depending on the specific outcome variable used (e.g., easier to detect effects for continuous vs binary variables), the cell sizes (smaller for interactions than for main effects), and the effect sizes, which are always difficult to estimate *a priori*. Table 1 shows power estimates for a sample of possible analyses under different assumptions.

Effect	Outcome variable	Assumed effect size across	Power to
		groups being compared	detect
Main effect of price	Purchase / receipt of any stove by	100% in P0 (N=70) vs 75% in	0.999
on adoption	household (binary)	P1 (N=84)	
		100% in P0 (N=70) vs 50% in	0.999
		P2 (N=140)	
Main effect of price	Reported use of stove on day prior to	50% in P0 (N= 70) vs 75% in	0.965
on stove use	survey (binary)	P2 (N=140)	
		(positive price effect)	

Table 1: Power to detect sample of possible treatment effects under different assumptions

Main effect of price on perceived quality	Continuous stove quality index (0 to 100) from Likert-scale questions (Assuming normal dist. with std. dev. of 25 pts)	75 pts in P1 (N=84) vs 65 pts in P0 (N=70) (positive price effect)	0.800
Main effect of peers on adoption	Purchase / receipt of any stove by household (binary)	75% in S2 (N=147) vs 60% in S1 (N=147) (negative peer effect)	0.838
Main effect of peers on perceived quality	Continuous stove quality index (0 to 100) from Likert-scale questions (Assuming normal dist. with std. dev. of 25 pts)	50 pts in S1 (N=147) vs 60 pts in S2 (N=147) (negative peer effect)	0.96

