Instrument-based measurements												
Data analysis												
Dissemination												
- Preparation of reports and peer-												
reviewed publications												
- Presentation at scientific												
conferences												
- Workshop in study area												

V. FUNDING

This research is being funded by the National Science Foundation's Economics program and the National Institutes of Health's Clean Cooking Implementation Science Network.

VI. ABOUT THE SUBJECTS

Component #1: P3 Bio

As shown in Figure 5, a total of 300 households will be enrolled in the P3 Bio component of the study. In each household, the primary cook (typically female, aged 18-55 years old) will serve as the main study participant. In households where another male household member makes financial decisions, we will conduct a secondary survey with this individual as well. We anticipate that all of these households will complete the study. The study population includes two main ethnic groups: Kasem and Nankam. The population will be split roughly evenly between these two groups.

Table 3: Subject Populations

Subject Population(s)	Number to be enrolled in each group
Group S1: Rural households from the same	150 households
clusters as REACCTING study households	

Group S2: Rural households from different150 householdsclusters from REACCTING study households150 households

Inclusion / Exclusion Criteria

Sample selection will proceed in two phases. First, clusters will be selected for inclusion in the study. All of the 25 REACCTING study clusters will be included to form the S1 group clusters. GIS mapping will then be used to *exclude* clusters that are close to those S1 clusters (using a buffer distance determined using preliminary data on social ties), and 25 S2 group clusters will then be randomly selected from the remaining clusters.

Second, the required number of households will be selected from each cluster. We will use the same inclusion and exclusion criteria used to select households in the existing REACCTING study. Using data from the district's demographic surveillance survey, a sample frame of eligible households will be created using the following inclusion criteria:

- Classified as "rural"
- Uses biofuel as main cooking fuel source
- Has woman in household aged 18-55 and at least one child under five (since women and children are the most vulnerable to cookstove smoke)

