S1 group households will be selected using GIS data to identify the *nearest neighbors*, meeting the above eligibility criteria, of each of the 6 REACCTING households that received stoves in that cluster during the REACCTING intervention phase. In the non-peer clusters, 6 seed households meeting the above eligibility criteria will be randomly selected, and then S2 group households will be selected as the nearest neighbors of those seed households. This procedure is used to create as similar as possible selection criteria and sampling methods between the peer (S1) and non-peer (S2) groups.

Component #2: P3 Gas

This component of the study involves two subject populations: LPG suppliers, and urban households. For the supply survey, all LPG refilling stations in the Upper East Region, and all retail shops selling LPG stoves or cylinders in the K-N Districts, will be eligible for inclusion in the study (16 businesses in total).

For the urban households, we will use the same demographic inclusion criterion as in the rural sample (at least one woman in household aged 18-55 and one child under five). As in the rural areas, we will first randomly select clusters from the urban area, and then randomly select households within each cluster, for a total of 300 households in this component. These subjects will complete an initial baseline survey (Activity 1.2) and will then be enrolled in the intervention (Activity 2.1) and follow up data collection. In the urban area, the majority of respondents belong to the Kasem ethnic group. As above, the primary cook is the primary participant, and if another individual in the household is responsible for making financial decisions for the household, this individual will also complete household surveys and will be present when stove offers are made.

VII. VULNERABLE POPULATIONS

> Not applicable.

VIII. RECRUITMENT METHODS

P3 Bio and P3 Gas Household Recruitment

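### Table 1's powers are best reproduced by treating households as independent, although price and peer exposure vary by cluster; alpha, sidedness, ICC and cluster-level inference are not stated

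*Combined protocol and SAP*

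**What the plan says.** **Unit of assignment.** On price, Section IV (Prices) states: "The price randomization will be done at the cluster level". Peer exposure also follows the cluster. For S1, Section VI says "All of the 25 REACCTING study clusters will be included to form the S1 group clusters"; for S2, Section IV (Peer Effects) says the "subgroup will consist of 25 clusters randomly selected from the area of the K-N Districts", beyond a buffer distance. Section VI adds that "a total of 300 households will be enrolled in the P3 Bio component of the study", 150 in each peer group, so 150 / 25 = 6 per cluster. This matches the selection rule: nearest neighbours of the 6 REACCTING households that received stoves in each S1 cluster, while in each S2 cluster "6 seed households meeting the above eligibility criteria will be randomly selected" and their nearest neighbours are taken.

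**Power.** Section IV (Analysis of Key Research Questions and Power Calculations) says: "Table 1 shows power estimates for a sample of possible analyses under different assumptions". The table lists household Ns, assumed rates or means, an SD of 25 points for the quality index, and a power for each row. The row for peers on adoption, for instance, assumes "75% in S2 (N=147) vs 60% in S1 (N=147) (negative peer effect") and prints 0.838. As drivers of power the text names outcome type, cell size and effect size. It gives no alpha, sidedness, ICC or design effect.

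**Analysis.** The same subsection begins its modelling plan with "Using the cluster-randomized assignment of selected households to different price treatments" and proposes reduced-form and possibly structural regressions. It mentions no clustered standard errors, random effects or cluster-level test. The cluster-level prior adoption and usage it mentions is an explanatory variable.

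**The concern.** When whole clusters share a price or a peer status, households in a cluster are not separate replicates of the treatment. If their outcomes are positively correlated, the effective sample is smaller than the household count and power is lower than a household-level formula gives.

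Some correlation is plausible. Households are near neighbours (Section VI), and they choose stoves at the end of a small group meeting (Section XII). Its size cannot be taken from the documents.

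Two things are at stake. Table 1 is the only power justification in the readable text, so a null result on peers, perceived quality or the interaction would be less informative than the table suggests. And if the regressions themselves ignored clustering, p-values and confidence intervals would be too favourable. That second consequence matters more, because it can still be settled at the analysis stage.

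**Working it through.** **Inputs (Table 1).** Price on adoption: 100% (70) v 75% (84), and 100% (70) v 50% (140). Price on use: 50% (70) v 75% (140). Price on quality: 75 (84) v 65 points (70), SD 25. Peers on adoption: 75% v 60%, 147 each. Peers on quality: 60 v 50 points, 147 each, SD 25. Interaction: 60% v 40% drop from 100% within P2, so 40% v 60% adoption, 70 each.

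**Formulas, independent households.**
- Proportions: power = Φ[(d − c − z·SE0) / SE1], where SE0 uses the pooled rate, SE1 the separate rates, and the continuity correction is c = ½(1/n1 + 1/n2).
- Means: power = Φ[d/SE − z], with SE = 25·√(1/n1 + 1/n2).
- z = 1.645 (one-sided 5%).

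**Reproducing the table.** Peers on adoption:
- SE0 = √(0.675 × 0.325 × 2/147) = 0.0546
- SE1 = √[(0.75 × 0.25 + 0.60 × 0.40)/147] = 0.0539
- c = 0.0068
- (0.15 − 0.0068 − 1.645 × 0.0546)/0.0539 = 0.99, so power is 0.839 against the printed 0.838.

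Price on quality: SE = 25·√(1/84 + 1/70) = 4.05; 10/4.05 − 1.645 = 0.83, so power is 0.796 against 0.800.

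All seven rows in table order, computed / printed: 0.999/0.999, 1.000/0.999, 0.964/0.965, 0.796/0.800, 0.839/0.838, 0.963/0.96, 0.714/0.7112. The largest gap is 0.004.

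**Adding clustering.** Replace each n by n/DE, with DE = 1 + (m − 1)·ICC and m = 6. ICC 0.05 gives DE 1.25; ICC 0.10 gives DE 1.50. These ICCs are assumptions. For peers on adoption at 0.05, n = 147/1.25 = 117.6, SE0 = 0.0611, SE1 = 0.0603, c = 0.0085, and (0.15 − 0.0085 − 1.645 × 0.0611)/0.0603 = 0.68, so power is 0.752.

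Like for like, one-sided 5%, ICC 0 / 0.05 / 0.10:

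| Row | With continuity correction | Without |
|---|---|---|
| Price on use | 0.964 / 0.919 / 0.866 | 0.974 / 0.942 / 0.902 |
| Peers on adoption | 0.839 / 0.752 / 0.674 | 0.868 / 0.794 / 0.727 |
| Interaction | 0.714 / 0.614 / 0.533 | 0.769 / 0.685 / 0.615 |
| Price on quality (means) | n/a | 0.796 / 0.714 / 0.646 |
| Peers on quality (means) | n/a | 0.963 / 0.923 / 0.876 |

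At ICC 0.01 the first column gives 0.956, 0.821 and 0.692, and the means rows 0.779 and 0.956: a loss of about 2 points or less. The price-on-adoption rows stay at or above 0.98 up to ICC 0.10. Keeping the correction on the actual rather than the deflated N gives 0.761 instead of 0.752 for peers on adoption at ICC 0.05. A simulation with a cluster-mean t-test, 25 v 25 clusters of 6, gives 0.80 / 0.72 for that row at ICC 0.05 / 0.10, close to the uncorrected figures.

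**Sidedness.** Two-sided 5% (z = 1.96), no correction, ICC 0 / 0.05: peers on adoption 0.787 / 0.692; price on quality 0.696 / 0.599; peers on quality 0.929 / 0.866; interaction 0.661 / 0.564. These four rows are already below print with no clustering. At two-sided 5%, no ICC of zero or more reproduces the table.

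**Type I error if clustering were ignored.** 2[1 − Φ(1.96/√DE)] for DE 1.25 / 1.50 / 2.00 (ICC 0.05 / 0.10 / 0.20) is 0.080 / 0.110 / 0.166.

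**The case against.** **Independence is inferred.** Because alpha is unstated, other settings can be tried. One-sided 10% with the continuity correction, m = 6 and ICC about 0.07 gives 0.949 (use), 0.801 (price on quality), 0.829 (peers on adoption), 0.953 (peers on quality) and 0.716 (interaction), all within 2 points of print. This stands: independence is not the only possible account. It is the better one, since it fits within 0.005 at a conventional 5%.

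**Stronger readings the documents do not support.**
- A reader might infer that the table's arithmetic is wrong. It is not; the figures reproduce. What is unstated is the assumptions.
- A reader might infer that the planned regressions will ignore clustering. The plan acknowledges cluster randomisation and is silent on standard errors, so the type I figures are conditional.
- A reader might argue that sharing a price makes households correlated. Price is the treatment; it creates no residual correlation within a price arm. Proximity and the group meeting are the relevant reasons.
- A reader might set the printed 0.838 against the uncorrected 0.794 and call the gap the cost of clustering. That mixes two changes. The like-for-like falls are 0.839 to 0.752 or 0.868 to 0.794.

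**Layout and timing.** The table's Ns are all multiples of 7 (147 = 21 × 7; 70, 84 and 140 = 10, 12 and 20 × 7), so 42 clusters of 7 may have been in mind. With m = 7, powers are about 1 to 4 points lower. Clusters per price level are not fixed; the Prices subsection leaves replicates to later modelling. Figure 5 and one short part of the text could not be read here. The table is offered only as a sample of analyses, and this version is dated January 2018 in a timeline ending August 2018. These points limit precision and urgency, but none supplies the missing alpha, ICC or inference method.

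**Conclusion.** The point holds as an unstated assumption that should be fixed. Table 1 is best explained by independent households at one-sided 5%, while both experimental factors vary by cluster. The overstatement depends on an ICC the documents do not give: about 2 points at 0.01, roughly 4 to 10 points at 0.05 for the peer, quality and interaction rows, and more at 0.10. The price-on-adoption conclusions are not threatened.

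Sidedness matters separately. Research question 3 in Section I asks whether peers raise or lower price elasticity, and Section II allows a peer effect of either sign, yet the table's apparent alpha is one-sided 5% or two-sided 10%.

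The evidence does not show that the study is too small or that its analysis will be invalid. The clustered figures rest on equal clusters of 6 and a normal approximation. The simulation check covers the peer layout only; rows with few clusters per price cell could do somewhat worse.

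**What to change.** 1. State that the price and peer regressions use standard errors clustered at the surveillance-survey (HDSS) cluster, with a small-cluster correction where a comparison rests on few clusters. This is the most consequential change.
2. State alpha and sidedness, two-sided for the peer and interaction questions.
3. Replace Table 1's power column with figures using 1 + (m − 1)·ICC, or cluster simulation, over a stated ICC range informed by REACCTING or pretest data. Use 25 + 25 clusters of 6 for the peer rows. For the price and interaction rows use the clusters per price level once set, or the counts implied by the table's Ns as a stated assumption. Say whether a continuity correction is applied.

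The cost is a recalculated table and a few sentences. No extra enrolment is proposed; the downside is that several stated powers become less favourable.

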- 3. How does peers' experience influence the relationship between price, on the one hand, and perceptions, technology adoption and use outcomes, on the other? Do peer effects increase or decrease the price elasticity of demand for the new technology?
- 4. How do perceptions of a technology change over time among households that adopt that technology initially? How do these perceptions relate to objective measures of stove performance (e.g., personal exposure to pollutants), and what is the relationship between perceptions and technology *use* over time?

II. BACKGROUND AND SIGNIFICANCE

[figure not shown]
Technology adoption continues be a central research topic in microeconomics because of its importance in understanding economic development and because of the kaleidoscope of models explaining different economic, psychological, and sociological factors at play. Two key strands of literature examine the roles of prices and peer effects on technology adoption.

Prices and technology adoption and use

Setting subsidy and end-user price levels for a new technology reflects a fundamental tension between rapid diffusion and sustainability (Mobarak et al. 2012; Dupas 2014). On the one hand, subsidizing adoption of socially beneficial technologies may be necessary to promote widespread adoption, at least in the short-run. Indeed, recent evidence has shown very high, and even discontinuous, price elasticities of demand for a number of low-cost health technologies in developing countries: new technologies offered at a positive price tend to exhibit much lower demand than identical products offered for free. The most recent World Development Report (World Bank 2015, see Figure 1) details numerous examples of this phenomenon. In one example that is particularly relevant for this proposal, Mobarak and coauthors (2012) analyze a field experiment with the distribution of cookstoves in Bangladesh. The researchers find demand for these modern stoves to be extremely price elastic, with only 5% of households purchasing the stoves with no discount and a 50% discount yielding 8-12% higher demand (relative to the full cost treatment).

On the other hand, many argue that goods given away for free or at low cost will be *used* at lower rates than goods for which users pay higher prices. There are at least two theoretical foundations for this hypothesis. First, price-based incentives for new technologies (or any scarce good) ensure allocation of

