In light of the previous research outlined above, Figure 2 presents our conceptual model using an influence diagram of how we expect prices, peers, and perceptions to interact, based on previous research. Prices can be expected to have both direct and indirect influences on key outcomes (technology adoption and use): The direct effect (the economic "law of demand") is expected to be negative, while it is possible that there is a positive indirect effect on both adoption and use via higher perceptions of technology benefits for higher-priced products. Peer effects can be expected to affect individual adoption and use through effects on individuals' perceived value of the new technology. This effect can be negative or positive.

Figure 2: Influence diagram of the factors of technology adoption dynamics. The solid arrows in the diagram are influences that this study will examine in detail. The dashed arrows are potential confounding feedbacks that our identification strategy will address. The signs in parentheses indicate whether effects are expected to be positive or negative, based on previous literature.

[figure not shown]
Importantly, the conceptual model in Figure 2 also highlights potential the feedbacks (the dashed arrows) that can confound causal identification, and which our experimental design seeks to address. First, a number of factors determine prices for a new technology in an observational setting, including supply and retail costs. We will address this confounding feedback using

prices which are randomly assigned across groups of households. Second, peer effects are well-recognized for their potential to generate positive feedback loops. We will control for this confounder by sampling households neighboring participants a previous study's cookstove intervention, in conjunction with the recruitment of new groups of households unexposed to the technology. This identification strategy for peer effects appears unique compared to previous research (Kremer and Miguel 2007; Bobonis and Finan 2009; Miller and Mobarak 2013).

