Interactive effect of peers' experience and price on adoption	Difference in purchase / receipt of any stove at high price between peer- exposed vs unexposed groups, assuming P0 adoption is 100% in S1 and S2	Within P2 group, 60% drop in demand in S1 (N=70) vs 40% drop in demand in S2 (N=70) (higher price elasticity within peer-exposed group)	0.7112

Component #2: Liquefied Petroleum Gas (LPG) - P3 Gas

Phase 1: Characterizing LPG Supply and Demand

Activity 1.1: LPG Supply Chain Analysis. Purpose: To describe the current LPG supply chain serving the K-N, including sources and costs of LPG stoves, cylinders, and fuel, and to analyze barriers and opportunities for scaling up and transforming the supply chain to expand access.

For this activity, we will identify all retail centers in the K-N selling LPG stoves or cylinders, as well as retail LPG filling stations throughout the Upper East region. Surveys will be conducted with all retail operators to measure: i) location (GPS coordinates), ii) type(s) of products sold; iii) hardware and fuel prices (measured at multiple time points to monitor price volatility); iii) sources of products and fuels supplying the retail center; iv) perceived problems or issues with the supply of products from the retailer's perspective, including uncertainty in supply or cost; v) perceived levels of demand in the local area and potential strategies for increasing demand, including price-related incentives and social or peer-to-peer marketing approaches; vi) potential opportunities and barriers for expanding operations into new areas, including peri-urban and rural areas; and v) potential for shifting to cylinder recirculation as opposed to the current cylinder refilling model.

Activity 1.2: LPG Demand Assessment. Purpose: To describe current patterns of LPG use for household cooking in the K-N, and to assess opportunities and barriers for expanding LPG adoption.

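### Table 1 gives no significance level or sidedness; its powers match one-sided 5% (equivalently two-sided 10%), and two-sided 5% lowers five of the seven by 3 to 12 points

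*Combined protocol and SAP*

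**What the plan says.** Section IV (Analysis of Key Research Questions and Power Calculations, Table 1) lists seven example comparisons, each with assumed effects, group sizes and a power. Two price-on-adoption rows are at 0.999. The other five are:

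- Price on stove use: 50% (N=70) vs 75% (N=140), power 0.965.
- Price on perceived quality: "75 pts in P1 (N=84) vs 65 pts in P0 (N=70) (positive price effect", SD 25, power 0.800.
- Peers on adoption: "75% in S2 (N=147) vs 60% in S1 (N=147) (negative peer effect", power 0.838.
- Peers on perceived quality: "50 pts in S1 (N=147) vs 60 pts in S2 (N=147) (negative peer effect", SD 25, power 0.96.
- Peers by price on adoption: "Within P2 group, 60% drop in demand in S1 (N=70) vs 40% drop in demand in S2 (N=70", power 0.7112.

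No significance level, sidedness or test is named. On the direction of peer effects, Section II (conceptual model) says "This effect can be negative or positive", and Section I, question 3, asks "Do peer effects increase or decrease the price elasticity of demand for the new technology". Section IV (Prices) says "The price randomization will be done at the cluster level". Section VI (Component #1) says "a total of 300 households will be enrolled in the P3 Bio component of the study", which Table 3 splits into 150 in S1 and 150 in S2.

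**The concern.** A power is defined only once the false-positive rate is fixed. A reader who finds none stated will usually assume two-sided 5%, and on that assumption five of the seven powers are too high.

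This matters most for the peer comparisons. The study sets out to learn whether peers raise or lower adoption, and whether they raise or lower price sensitivity. A one-sided test in the negative direction could not detect the positive effect the protocol also considers possible. The table shows the main peer effect on adoption above the usual 0.80 mark; whether the design reaches that mark depends on the missing significance level.

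**Working it through.** **Inputs.** Effects, group sizes and the SD of 25 are taken from Table 1. In the peer-by-price row, adoption at the zero price is assumed to be 100%, so drops of 60% and 40% mean adoption of 0.40 vs 0.60. Critical values are z = 1.645 (one-sided 5% or two-sided 10%) and z = 1.960 (two-sided 5%).

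**Mean rows.** Power = Φ(δ − z), with δ = difference / [SD·√(1/n₁ + 1/n₂)].

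- Price on quality: δ = 10/[25·√(1/84 + 1/70)] = 2.472. Φ(2.472 − 1.645) = 0.796 and Φ(2.472 − 1.960) = 0.696. Stated: 0.800.
- Peers on quality: δ = 10/[25·√(2/147)] = 3.429. Φ(1.784) = 0.963 and Φ(1.469) = 0.929. Stated: 0.96.

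The noncentral t gives 0.793 and 0.690 for the first row, 0.962 and 0.928 for the second. These two rows involve no choice of binary formula.

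**Binary rows.** Power = Φ[(|p₁ − p₂| − c − z·SE₀)/SE₁], where SE₀ = √[p̄(1 − p̄)(1/n₁ + 1/n₂)], SE₁ = √[p₁(1 − p₁)/n₁ + p₂(1 − p₂)/n₂], and c = (1/n₁ + 1/n₂)/2 is the continuity correction.

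- Peers on adoption: p̄ = 0.675, SE₀ = 0.05463, SE₁ = 0.05393, c = 0.00680. At 1.645: (0.15 − 0.00680 − 0.08987)/0.05393 = 0.989, power 0.839. At 1.960: (0.15 − 0.00680 − 0.10707)/0.05393 = 0.670, power 0.749.
- Peers by price: p̄ = 0.50, SE₀ = 0.08452, SE₁ = 0.08281, c = 0.01429. The arguments are 0.564 and 0.242, powers 0.714 and 0.596.
- Price on use: p̄ = 0.667, SE₀ = 0.06901, SE₁ = 0.07008, c = 0.01071. The arguments are 1.795 and 1.485, powers 0.964 and 0.931.

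| Row | Stated | z = 1.645 | z = 1.960 | z = 1.960, no correction | One-sided alpha implied by stated power |
|---|---|---|---|---|---|
| Price on use | 0.965 | 0.964 | 0.931 | 0.949 | 0.0518 |
| Price on quality | 0.800 | 0.796 | 0.696 | n/a | 0.0515 |
| Peers on adoption | 0.838 | 0.839 | 0.749 | 0.787 | 0.0497 |
| Peers on quality | 0.96 | 0.963 | 0.929 | n/a | 0.0466 |
| Peers by price | 0.7112 | 0.714 | 0.596 | 0.661 | 0.0493 |

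The two 0.999 rows hardly move. For 100% vs 75% the power goes from 0.999 to 0.997, and for 100% vs 50% it stays above 0.999.

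**Role of the correction.** Without it, one-sided 5% gives 0.974, 0.868 and 0.769 for price on use, peers on adoption and peers by price, all above the stated values. Fisher's exact test, one-sided 5%, gives 0.964, 0.840 and 0.728. The corrected formula is therefore the one that reproduces the column.

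**Consequence for peers on adoption.** Keeping 0.838 at two-sided 5% needs 181 households per group with the correction, or 168 without it, against 147 tabulated and 150 planned. Reaching 0.80 needs 165 with the correction. At 147 per group, the difference would have to be about 17 points instead of 15.

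**Clustering, as an illustration.** With 150/25 = 6 households per cluster and an assumed intracluster correlation of 0.05, the design effect is 1 + 5 × 0.05 = 1.25 and the effective size is 147/1.25 = 117.6 per group. Peers on adoption is then about 0.75 at one-sided 5% and 0.64 at two-sided 5%. The 0.05 is an assumption; the documents give no value.

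**The case against.** The strongest reply is that no number in the table is wrong: the column is consistent with one significance level to within half a point, and only a label is missing. All five affected rows are written with an assumed direction, which leaves a one-sided reading open, and no section promises two-sided 5%. The research questions describe what is to be learned; they do not specify a test.

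That reply stands in part. It holds for the two price rows, where I rely only on the arithmetic. It does not hold for the three peer rows, because a direction assumed for a power calculation is not a commitment to test only that way, and the protocol's own questions run both ways.

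The 3-to-12-point range also depends on a continuity correction that the protocol does not name. Uncorrected, the shortfall over the five rows is 1.6 to 10.4 points, and price on use is then close to its stated value. This caveat is fair but does not change the conclusion: the two mean rows need no correction, and peers on adoption falls below 0.80 either way.

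Finally, the table is offered as illustrative, its group sizes total 294 where 300 are planned, and price levels and replicates are to be settled later. All true. But these are the only powers the documents give for P3 Bio, and later choices about price replicates do not alter the S1 and S2 totals behind the main peer rows.

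**Conclusion.** The concern holds. The significance level and sidedness are not stated, and the powers correspond to one-sided 5% or, equally, two-sided 10%; the arithmetic cannot separate the two. As a set they are not two-sided 5% powers. On the formulas that reproduce the table, moving to two-sided 5% costs 3.4 points for price on use, 10.4 for price on quality, 9.0 for peers on adoption, 3.1 for peers on quality and 11.6 for peers by price.

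The loss for the three binary rows assumes the continuity correction; the loss for the two mean rows does not. All these figures treat households as independent, so any positive intracluster correlation lowers them further. The point should be fixed, but it does not by itself invalidate the design.

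**What to change.** Above Table 1, state the test and a two-sided significance level of 0.05. If one-sided testing or a 10% level was intended, say so and justify it row by row, in particular for the peer comparisons. Recompute the power column to match, and show it over a stated range of assumed intracluster correlations, since price is assigned by cluster and the S1/S2 contrast is also between clusters.

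The cost is a sentence or two and a recalculated column. No extra enrolment is required; the stated powers simply become less favourable.
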